6.6.4	Data Review	26
6.7	RECORD MAINTENANCE	27
6.7.1	Records	27
7	REPORTS (INCLUDES ANNUAL REPORTS, FINAL REPORTS FROM INVESTIGATOR AND SPONSOR)	27
7.1.1	Reports	27
7.1.2	Investigator's Final Report	28
7.2	INVESTIGATIONAL SITE MONITORING PROCEDURE	28
7.3	LABELING: INSTRUCTIONS FOR USE.....	28
7.4	DEVIATIONS FROM PROTOCOL	28
7.5	INVESTIGATIONAL SITE TERMINATION.....	28
	ATTACHMENT A: SAFETY ALGORITHM	29

PROTOCOL SUMMARY

Title:	Esteem® Totally Implantable Hearing System Post-Approval Study
Purpose:	To evaluate the safety and efficacy of the Esteem® Totally Implantable Hearing System (hereafter called the Esteem® System) implanted by newly-trained surgeons in subjects suffering from moderate to severe hearing loss.
Trial Design:	
The Post-Approval Study is similar to the PMA pivotal clinical trial, which was designed as a prospective, multi-center, non-randomized, clinical trial to evaluate the safety and efficacy of the Esteem® System. For this trial the subject acts as his or her own control.
 
This trial has been designed to meet the United States' regulatory requirements.

Enrollment Size:	A minimum total of 45 new subjects will be enrolled and implanted in this study, with the requirement of 45 evaluable subjects for analysis of efficacy endpoints. For safety endpoints, a minimum of 109 evaluable subjects will be required.
Subject Population:	Subjects 18 years of age and older who have moderate to severe sensorineural hearing loss (HL) defined by PTA, have a healthy middle ear, have an unaided speech discrimination score of equal to or better than 40%, and have previously worn a hearing aid for a minimum of 30 days are eligible for inclusion in the Post Approval Study. See detailed inclusion/exclusion criteria for specifics.
Questions:	
The following questions are to be answered:
 
 • Is the Esteem® effective through 1 year follow-up? • Is the Esteem® safe through 1 year follow-up? • Is the incidence of facial pareses/paralysis at 1 month follow-up no greater than 7%?
Primary Objectives:	

1. To demonstrate that the *Esteem® System* improves the speech threshold of sensitivity for hearing and identifying speech signals as well as or better than the pre-implant hearing aid (aided condition).

Endpoint: Comparison of the speech reception threshold (SRT) using the *Esteem® System* as compared to the pre-implant aided condition.

2. To demonstrate that the *Esteem® System* is as effective as or better than the hearing aid for improving speech discrimination (intelligibility) as shown by the word recognition score at 50 dB.

Endpoint: Comparison of the word recognition score using the *Esteem®* compared to the pre-implant aided condition.

3. To determine the incidence of Serious Adverse Device Effects (SADE) and Adverse Device Effects (ADE) and the incidence rate of device failures and replacements.

Endpoint: The analysis of the incidence of SADEs and device failures and replacements at each follow-up.

4. To demonstrate that the incidence of facial pareses/paralysis is no greater than the 7% incidence experienced in the PMA clinical trial.

Endpoint: The analysis of the incidence of facial pareses/paralysis at 1 month follow-up.

5. To demonstrate that the subjects' cochlear function remains unchanged with the *Esteem® System* as shown by comparison of the subjects' pre-implant baseline bone conduction threshold versus the subjects' post-activation visit bone conduction threshold.

Endpoint: Comparison of bone conduction threshold (BC) using forehead placement post activation compared to the pre-implant BC threshold.

Secondary Objectives:

1. To show that the *Esteem® System* improves Quality-of-Life when compared to the baseline aided condition as shown by APHAB results.
2. To gather subject feedback and comments on the use of the *Esteem® System* relative to the pre-implant hearing aid (aided condition) as shown by the *Esteem® Questionnaire*.

Sponsor Contact Information:

Envoy Medical Corporation, Inc. (EMC)

[name]

[name]

[contact]

Customer Service [contact]

www.envoymedical.com

Changes in Revision 04

Change footer revision number from Rev 03 to Rev 04
Clarify the enrollment totals for efficacy and safety endpoints in Protocol Summary, sections 1.4, 2.2 and 4.7
Change sponsor address of Envoy Medical Corporation to current address
Miscellaneous typo corrections

1 INTRODUCTION

1.1 Device Name

The device being evaluated in this Post Approval Study is the *Esteem®* Totally Implantable Hearing System (*Esteem® System*). The *Esteem®* has recently been approved by FDA for the US market under PMA P090018. This study fulfills the requirement for one of the Post Approval Studies.

1.2 Device Description and Principle of Operation

The *Esteem® System* is a totally implantable hearing system designed to improve hearing in subjects suffering from moderate to severe hearing loss that is sensorineural in origin.

The *Esteem® System* consists of three components that are implanted in the subject: A Sound Processor (SP) is implanted under the scalp over the temporal bone and is connected via leads to two piezoelectric transducers (called the Driver and Sensor), which are implanted in the middle ear. In addition there are two components that will be used during the implant of the *Esteem® System*: An intra-operative test system, and the *Esteem®* programmer. The *Esteem®* programmer will also be used by the audiologist for follow-up *Esteem® System* management. When the *Esteem® System* is activated the subject will receive an additional external component, the Personal Programmer. See full description below.

The *Esteem® System* works in the following manner: The Sensor is placed on the incus bone. This Sensor senses mechanical vibrations transmitted from the eardrum through the malleus and/or incus bone, then converts these vibrations into an electrical signal, which is sent to the SP. The SP amplifies and filters the signal, then sends it to the Driver, which has been attached to the head of the stapes. The Driver converts the modified electrical signal back to mechanical vibrations that is transferred to the stapes. The stapes bone vibrates the oval window, which produces pressure waves in the fluid of the cochlea. The cochlea converts the pressure waves to nerve impulses, which are transmitted via the eight cranial nerves to the brain, where they are interpreted as sound.

Prior to implantation of the Driver and Sensor, the incus will be separated from the stapes at the incudostapedial joint and 1 to 3 mm will be resected from the long process of the incus. This will allow the Driver to be placed directly over the stapes bone and prevent feedback to the Sensor that could result in poor system performance.

The *Esteem®* programmer enables the physician and/or the audiologist to program each subject's implanted SP to that subject's specific audiological need. The programmer is also used to interrogate the *Esteem® System*'s Sound Processor and provides the physician and/or the audiologist with diagnostic capabilities both during the operative procedure and during follow-up clinic visits.

The Personal Programmer enables the subject to select from three (3) pre-set programs for background noise levels, to place the device on standby, and to increase or decrease the volume of his/her *Esteem® System* SP using radio frequency (RF) telemetry. The Personal Programmer is battery operated and has a low battery indicator.

The Envoy Medical Intra-operative System Analyzer (ISA) is used during the implant procedure to verify that the Sensor and Driver are positioned correctly. It will also be used at the end of the implant procedure to verify that the *Esteem® System* is functioning appropriately.

1.2.1 Anticipated Changes in Device

There are no plans to change the device or the protocol during this Post Approval Study.

1.3 Indications for Use

The *Esteem®* is intended to alleviate hearing loss in patients by replicating the ossicular chain and providing additional gain. The *Esteem®* is indicated for patients with hearing loss that meet the following criteria:

- 18 years of age and older
- Stable bilateral sensorineural hearing loss
- Moderate to severe sensorineural hearing loss as defined by Pure Tone Average (PTA)
- Unaided Speech discrimination scores greater than or equal to 40%
- Normally functioning Eustachian tube
- Normal middle ear anatomy
- Normal Tympanic Membrane
- Adequate space for *Esteem®* implant determined via a high resolution CT scan
- Minimum of 30 days of experience with appropriately fit hearing aids

1.4 Justification for the Investigation

In order to study the safety and effectiveness of the *Esteem® System* in a clinical environment, a post-approval study was requested by FDA. This post-approval study will include a minimum of 45 subjects implanted by newly-trained surgeons at 5 to ten investigational sites followed through their 1-year follow-up visit for both safety and efficacy endpoints. In addition, an extension of the PMA pivotal clinical trial conducted under IDE G070162 was conducted as a separate post-approval study. That study demonstrated long-term safety and effectiveness through 5-year follow-up.

1.5 Duration of the Investigation

The post-approval study will commence immediately upon PAS Protocol approval. Subjects will be followed at 1, 4 and 10-months post-activation and annually thereafter through 1 year.

2 STUDY DESIGN AND OVERVIEW**2.1 Trial Design**

This Post Approval Study is designed as a prospective, multi-center, non-randomized, clinical trial to evaluate the safety and efficacy of the *Esteem® System* implanted by newly-trained surgeons. For this trial the subject will act as his or her own control.

This trial has been designed to meet United States' regulatory requirements.

Each subject will act as both the test subject and the control by being tested prior to implant in both the unaided and aided condition.

2.2 Investigational Sites and Number of Enrollments

The post-approval study will enroll a minimum of 45 new subjects on a consecutive consenting basis at 5 to 10 investigational sites to be implanted by newly-trained surgeons. These subjects will be evaluated for both efficacy and safety endpoints. The goal will be to monitor the subjects through their one (1) year follow-up. NOTE: In order to achieve the required sample size of 109 subjects for the safety endpoints, data from these 45 new subjects will be supplemented by data from a retrospective chart review of "commercial" (non-study subjects).

Trial Objectives

The overall objective of the study is to evaluate the safety and effectiveness of the *Esteem® System* implanted by newly-trained surgeons in subjects suffering from moderate to severe hearing loss.

Primary Objectives:

- 1) To demonstrate that the *Esteem® System* improves the speech threshold of sensitivity for hearing and identifying speech signals as well as or better than the pre-implant hearing aid (aided condition).
Endpoint: Comparison of the speech reception threshold (SRT) using the *Esteem® System* as compared to the pre-implant aided condition.
- 2) To demonstrate that the *Esteem® System* is as effective as or better than the hearing aid for improving speech discrimination (intelligibility) as shown by the word recognition score at 50 dB.
Endpoint: Comparison of word recognition score using the *Esteem®* as compared to the pre-implant aided condition.
- 3) To determine the incidence of Serious Adverse Device Effects (SADE) and Adverse Device Effects (ADE) and the incidence rate of device failures and replacements.
Endpoint: The analysis of the incidence of SADEs and device failures and replacements at each follow-up.
- 4) To demonstrate that the incidence of facial pareses/paralysis is no greater than the 7% incidence experienced in the PMA clinical trial.
Endpoint: The analysis of the incidence of facial pareses/paralysis at 1 month follow-up.
- 5) To demonstrate that the subjects' cochlear function remains unchanged with the *Esteem® System* as shown by comparison of the subjects' pre-implant baseline bone conduction threshold versus the subjects' post-activation visit bone conduction threshold.
Endpoint: Comparison of the bone conduction threshold with forehead placement compared to the pre-implant bone conduction threshold.

Secondary Objectives:

- 1) To show that the *Esteem® System* improves Quality-of-Life when compared to the baseline aided condition as shown by APHAB scores.
- 2) To gather subject feedback and comments on the use of the *Esteem® System* relative to the pre-implant hearing aid (aided condition) as shown by the *Esteem®* Questionnaire.

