4.7 Adverse Events

The 109 subjects to be reported for the Adverse Event endpoint will consist of the 45 newly-implanted subjects supplemented by data from a retrospective chart review of "commercial" (non-study subjects).

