4.7.2 Reporting of Adverse Events

The procedure for reporting any AE is as follows:

- All Adverse events will be documented on an Adverse Event Form
- The Investigator is responsible for reporting AEs to his or her IRB in accordance to their site's IRB procedures.
- The Investigator shall report all unanticipated adverse device effect to the Monitor/Sponsor as soon as possible, but definitely no later than 10 days after obtaining knowledge of event.
- The Sponsor is responsible for informing the FDA, all reviewing IRBs and other investigators of any unanticipated adverse device effect that has occurred.

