5 STATISTICAL ANALYSIS

5.1 Sample Size

For the effectiveness objectives, based upon the following analysis and 0204 clinical data, a sample size of 45 new subjects meets the guidelines for statistical power. For the facial pareses/paralysis objective with an end point of 1 month, a sample size of 109 subjects is required as shown below.

SRT

Based on a mean improvement in SRT over hearing aid of 10 dB and a standard deviation of 13 dB, 45 subjects at 1 year would provide at least 80% power for testing non-inferiority and superiority at a one-sided 0.05 alpha level. A margin of – 5 dB will be used for non-inferiority and a margin of +5 dB will be used for superiority.

WRS

Based on a mean improvement in WRS over hearing aid of 22% and a standard deviation of 31, 45 subjects at 1 year would provide at least 80% power for testing non-inferiority and superiority at a one-sided 0.05 alpha level. A margin of –10% will be used for non-inferiority and a margin of +10% will be used for superiority.

Facial Pareses/paralysis:

Based upon a null hypothesis of 7% and a hypothesized true rate of 2% of facial paresis/paralysis, 109 subjects at 1 month would provide at least 80% power for testing the hypothesis.

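### The facial paresis test may draw up to 64 of its 109 subjects from commercial charts with no stated surgeon or selection rule and no by-source result, so it is not shown to answer the newly-trained-surgeon question

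*Combined protocol and SAP*

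**What the plan says.** The Protocol Summary gives the purpose as evaluating the device "implanted by newly-trained surgeons in subjects suffering from moderate to severe hearing loss". Section 2.1 and the overall objective under section 2.2 say the same. Section 1.4 ties the surgeon description to the prospective group: "This post-approval study will include a minimum of 45 subjects implanted by newly-trained surgeons at 5 to ten investigational sites". Section 2.2 adds that these subjects are enrolled consecutively as they consent.

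The safety total is larger. The Protocol Summary states: "For safety endpoints, a minimum of 109 evaluable subjects will be required". Section 2.2 explains how that number is reached: "data from these 45 new subjects will be supplemented by data from a retrospective chart review of" commercial patients outside the study. Section 4.7 repeats the arrangement: "The 109 subjects to be reported for the Adverse Event endpoint will consist of the 45 newly-implanted subjects supplemented by data" from the same chart review. These two places hold all the text on the chart cohort. Neither says who operated, over what period, or how charts are chosen.

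Section 5.1 sets a null rate of 7% and an assumed true rate of 2%, and says that "109 subjects at 1 month would provide at least 80% power for testing the hypothesis". Section 5.2, Objective 4, compares the one-sided 95% exact binomial upper bound with 7% and declares success if the bound is lower. It plans no estimate by source.

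**The concern.** Objective 4 is the only safety objective with a numeric study-level pass criterion, and facial paresis is one of the three questions in the Protocol Summary. At minimum enrolment, most of the subjects in that test come from a cohort that the plan does not define. If the chart patients have a different event rate from the prospective ones, the pooled result can pass when the newly-trained-surgeon implants do not support it, or fail when they do. Nothing in the planned analysis would let a reader see which has happened. A selection rule also loses credibility if it is written after the charts have been read, so it has to be fixed first.

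**Working it through.** **Inputs.** Prospective minimum 45 (2.2). Safety total 109 (Protocol Summary, 2.2, 4.7, 5.1). Null 7%, assumed true rate 2%, power at least 80% (5.1). One-sided 95% exact upper bound below 7% (5.2).

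**Step 1: the plan's own figure.** The one-sided 95% Clopper-Pearson upper bound for x events in n is the 0.95 quantile of Beta(x+1, n−x).

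- 3/109 gives 6.96% (pass); 4/109 gives 8.20% (fail). Success therefore means at most 3 events.
- Exact alpha: P(X ≤ 3 | 109, 0.07) = 4.85%.
- Power: P(X ≤ 3 | 109, 0.02) = 82.5%.
- At n = 108 only 2 events are allowed and power is 63.3%, so 109 is the smallest n that reaches 80%.

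The plan's 109 is reproduced and is correct.

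**Step 2: share from charts.** 109 − 45 = 64, and 64/109 = 58.7%. This is the most for a total of 109. Section 4.2 keeps subjects who miss the hearing-aid fit criterion in the safety set, so prospective numbers can exceed 45 and charts can fall below 64.

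**Step 3: sensitivity of the pooled test.** With a events among the 45 prospective subjects at rate p and the rest among 64 charts at rate q:

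P(pass) = Σ (a = 0 to 3) P(A = a | 45, p) × P(C ≤ 3 − a | 64, q)

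The documents give no rate by source, so p and q are assumptions.

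- p = 7%, q = 2%: 0.0382×0.9606 + 0.1293×0.8634 + 0.2141×0.6329 + 0.2310×0.2745 = 0.347.
- p = 2%, q = 7%: 0.4029×0.3365 + 0.3700×0.1657 + 0.1661×0.0559 + 0.0486×0.0096 = 0.207.

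| Assumed chart rate | P(pass), prospective 7% | P(pass), prospective 2% |
|---|---|---|
| 10% | 1.1% | 5.9% |
| 7% | 4.8% | 21% |
| 4% | 17% | 54% |
| 2% | 35% | 82.5% |
| 0% | 61% | 99% |

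More prospective subjects shrink the effect. With an illustrative split of 80 and 29, 7%/2% gives 13% and 2%/7% gives 51%.

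**Step 4: a concrete case.** Three events in 45 is 6.7%, with an upper bound of 16.3%. Add 0 in 64 charts and the pooled result is 3/109, bound 6.96%: a pass.

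**Step 5: what 45 alone can show.** 0/45 gives a bound of 6.44%; 1/45 gives 10.1%. A pass needs 0 events, and power at 2% is 0.98^45 = 40%. A test on the prospective subjects alone therefore cannot replace the pooled one.

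**The case against.** Four points on the other side deserve weight.

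- *The target population is inferred.* Objective 4 names only the 7% benchmark, and section 2.2 openly says that commercial patients will be included. The test could be meant for a broader population. That stands in part. But the purpose, the design and the overall objective all name newly-trained surgeons, so the plan should say which population Objective 4 describes.
- *No mismatch is shown.* A reader might infer that the chart patients were operated on by more experienced surgeons and that pooling favours a pass. The documents do not say who implanted them; it may have been newly-trained surgeons as well. The bias, if any, could run either way.
- *Event capture is not shown to be weaker in charts.* A reader might infer that study events are fully recorded while chart events are not. The text does not establish this. The rule "All Adverse events will be documented on an Adverse Event Form" sits under section 4.7, whose opening covers all 109. Table 1 lists no facial-nerve examination for prospective subjects, no case definition is given for anyone, and the 1-month point in Objective 4 is not tied to surgery, while section 4.5.3 counts visits from activation. The gap in definition is study-wide.
- *Reporting by source has little power.* A two-sided Fisher test of 45 at 7% against 64 at 2% has about 15% power. That is right, so the selection rule is the main remedy and separate bounds are for description only.

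**Conclusion.** The concern holds as a cheap improvement that should be made. The plan permits a chart cohort of up to 64 of 109 that need not match the study's question, and no planned analysis would reveal it. Because the test turns on 3 versus 4 events, the outcome is sensitive to that cohort: for a prospective rate of 7%, the chance of passing runs from 1.1% to 61% as the assumed chart rate goes from 10% to 0%. These sizes rest entirely on assumed rates. If both cohorts share one rate and events are captured equally, the test performs as designed, with alpha 4.8% and power 82.5%.

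A reader might go further and conclude that the test is invalid or that 109 is the wrong number. The documents support neither: the sample size is reproduced exactly, and no rate difference between the sources is stated anywhere.

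**What to change.** 1. In sections 2.2 and 4.7, define the chart cohort as all consecutive commercial implants by newly-trained surgeons that meet the labelled indications in section 1.3, within a pre-specified period. Select them without sight of outcomes, and fix the total in advance (the Protocol Summary gives 109 only as a minimum). Define newly-trained once for both cohorts; section 6.4 describes the training but not how long the term applies. If too few such charts exist, word the Objective 4 conclusion for the pooled population.
2. In section 5.2, Objective 4, report the prospective and chart cohorts separately with exact bounds beside the pooled test, labelled as descriptive.
3. Set one facial paresis/paralysis case definition and one time window with a stated starting point, and apply both to both cohorts. Report how many selected charts lack documented facial-nerve status in that window.

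The cost is protocol wording and a chart-selection rule. No further prospective subjects are needed, and the total of 109 and its power are unchanged. The downside is that more charts may have to be reviewed to find enough eligible cases.

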3 BENEFITS/RISKS

Sponsor and the investigators have determined that the study is justified because the potential benefits outweigh the attendant risks. This has been confirmed by FDA in approving PMA P090018.

3.1 Potential Benefits

Hearing aids, cochlear implants, and semi-implantable hearing prostheses are some of the technologies available for the treatment of hearing loss. The *Esteem® System* has been developed as a fully implantable treatment option for adults who have hearing loss. The potential benefits that the *Esteem® System* may provide include:

- Better fidelity of sound
- Elimination of ear canal occlusion
- Elimination of maintenance issues associated with hearing aids, cochlear implants and semi-implantable hearing
- Improved cosmesis
- Improved ease of communication
- Improved audiometric thresholds
- Improved hearing in noise

devices

- Elimination of hearing aid type feedback
- Elimination of intolerable ear canal conditions such as eczema or infections caused by hearing aids
- Ability to hear continuously throughout the day (24/7).

- Improved hearing in reverberating rooms
- Longer battery life than hearing aids
- Reduction of the stigma of hearing impairment
- Improved quality of life
- Regain active lifestyle

